Our study will implement the caregiver survey and the medical record abstraction tools in the PFK ABD population. Caregivers of all 8,080 newly enrolled ABD children will be invited to participate in the survey. We estimate that our methods will yield 2,750 caregiver survey respondents. The estimated 34% response rate considers a combination of those who are unreachable based on available contact information and those who are reached but who opt out of participation. This sample size will allow us to estimate performance on each survey-based care coordination indicator within a 95% confidence interval of ± 1.5 percentage points (conservatively assuming underlying performance of 50%). Confidence interval widths for age, gender, and urban/rural subpopulations will range from ± 1.8 to ± 3.7 . This sample size will allow us to identify a significant urban/rural difference ($\alpha=0.05$) of 0.05 percentage points (i.e., 0.50 vs. 0.55) with a power of 0.83.

Medical Record Abstraction

Participants & Sample Size

We further estimate that 1,000 of those who complete the survey will consent to a review of their medical records that will allow data collection on medical record review based measures that can be linked to survey data and ultimately medical claims data. This consent rate is based on experience in current pilot work. This sample size will allow us to estimate performance on each medical record-based care coordination indicator within a 95% confidence interval of ± 2.9 percentage points (conservatively assuming underlying performance of 50%). Confidence interval widths for age, gender, and urban/rural subpopulations will range from ± 3.6 to 7.0. This sample size will allow us to identify a significant urban/rural difference ($\alpha=0.05$) of 0.10 percentage points (i.e., 0.50 vs. 0.60) with a power of 0.89.

Analysis

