We will first calculate performance on each of the 31 care coordination measures using data from the FECC and the care coordination medical record review. We will stratify indicator performance by age group, urban/rural residence, and disabling diagnosis (physical vs. mental diagnosis). Where appropriate, performance in our sample will be compared with pilot data collected by COE4CCN. We will then link data from the FECC, the medical record review, and the PFK claims data, at the individual level, to assess the relationship between receipt of care coordination elements and selected outcomes. For example, this linked database will allow us to test the relationship between receipt of a useful and understandable discharge summary following an inpatient stay and 30 day readmission or the relationship between regular communication with a designated care coordinator and use of the emergency department. Specific quality/outcomes measures to be studied will be drawn from claims and EMR-based CHIPRA and HEDIS measures with input from our advisory panel. We expect limited missing data in the survey and medical record data due to our data collection methods. Missing data from the survey and the medical record review will be handled using the “available case

analysis approach” in which all cases with complete data for a selected analysis are included in that analysis.

The proposed analysis in Aim 2 will allow us to 1) quantitatively assess the quality and completeness of care coordination offered to ABD children upon roll-in to the ACO; 2) determine whether that quality and completeness is consistent across selected subpopulations; and 3) understand the relationships between elements of care coordination and patient-centered measures of quality and outcomes.

Aim 3

In Aim 3, we will compare quality, utilization, and other patient-centered outcomes for ABD children before and after joining an ACO in Ohio using claims, survey and medical record data. Our comparative analysis includes both quantitative and qualitative measures identified through Aims 1 and 2. In addition, we will triangulate findings from our quantitative, qualitative and care coordination assessment analyses to provide a robust and multi-faceted analysis of the comparative effectiveness of care coordination under a fee-for-service system compared to an ACO model for children with disabilities.

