The Patient Advisory Panel will assist us in developing our final dissemination plan. The patient-centered quality of the research will ensure that the findings disseminated to policy-makers and providers also emphasize patients and caregivers, alerting them to the importance of these groups in their decision-making going forward. The results of our research might be disseminated through various stakeholder groups, including families of disabled children, child disability advocacy groups, state Medicaid agencies, policy makers and ACO and health system leaders. In addition to the dissemination activities included in our proposal, the results of this research could be disseminated through stakeholder newsletters, webinars, websites, patient or community conferences, news media outlets and issue briefs. Target stakeholder meetings and conferences will include the AcademyHealth Annual Research Meeting and National Health Policy Conference and the Pediatric Academic Societies/Ambulatory Pediatrics Association Complex Care Special Interest group meeting, Target journal for publication will include *Health Affairs* and *Pediatrics*.

The results of this research have real potential to be implemented in other settings, namely in other ACOs. In the wake of the Affordable Care Act, ACOs are developing across the country. Medicare ACOs have largely dominated the ACO market, however, there is increasing interest and growth in Medicaid and pediatric ACOs. Our research involves one of the most highly regarded pediatric ACOs in the country and pediatric ACOs across the state of Ohio and elsewhere are likely to look to results from our research to help guide their care coordination efforts for ABD children.

Collaborating Organizations, Personnel, Project Roles

University of North Carolina at Chapel Hill

[name], Associate Professor, will serve as Principal Investigator. As such she will lead the project's efforts and assumes overall responsibility for completing project milestones according to the PCORI contract.

[name]., Professor, will serve as Co-Investigator with primary responsibility for Aim 3. She will work together with [name] of OSU to conduct quantitative comparative analyses using survey, medical record, and claims data. She will also contribute to the quantitative analyses under Aim 2 and the cross-aim analyses under Aim 3.

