ATTACHMENT B

Detailed Measure Specifications and Scoring for FECC Caregiver Survey Indicators

All are on 0-100 scale, where higher is better. Survey response items should be coded to reflect that. For dichotomous items, "no" = 0 and "yes" = 100. More specific instructions are included where applicable in Scoring Notes.

All screener items must be nonmissing for a dependent item to be scored

If items are part of a yes/no checklist, if at least one item is answered, impute "no" for skipped items in mailed surveys or "don't know" for telephone surveys (but not for items that telephone respondents refused to answer).

Otherwise, all component items must be nonmissing for a multi-item indicator to be scored.

MP=Main Provider

Indicator ID	Indicator Description	Eligible	Survey Item	Scoring notes
CARE COORDINATION SERVICES				
CC2	Caregivers should report that their child has a designated care coordinator.	Q2=1 (Child visited more than one doctor's office or used more than one kind of health care service in last 12 months)	Q3 (Someone in MP's office helped manage child's care or treatment from different doctors/providers)	
CC3	Caregivers who report that their child has a designated care coordinator (as identified in CC2) should report that they know how to access their care coordinator.	Q2=1 (Child visited more than one doctor's office or used more than one kind of health care service in last 12 months), Q3=1 (Someone in MP's office helped manage child's care or treatment from different doctors/providers)	Q6 (Knew how to contact person who helped manage child's care when you needed help or had a question)	
CC5	Caregivers who report having a designated care coordinator (as identified in CC2) and who require community services should also report that their care coordinator helped their child to obtain needed community services in the last year.	Q2=1 (Child visited more than one doctor's office or used more than one kind of health care service in last 12 months), Q3=1 (Someone in MP's office helped manage child's care or treatment from different doctors/providers), Q15=1 (Caregiver or child needed or used community services in last 12 mos)	Q16(Person in MP's office who helped manage child's care helped get community services)	

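### Aim 2 survey power of 0.83 for urban vs rural appears to rest on an undeclared finite population correction; an ordinary two-sided test reaches at most 0.75

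*Combined protocol and SAP*

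**What the plan says.** All figures are in Aim 2, under the two Participants & Sample Size headings.

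- **Caregiver Survey.** Caregivers of all 8,080 children are invited and 2,750 responses are expected. The plan will "estimate performance on each survey-based care coordination indicator within a 95% confidence interval of ± 1.5 percentage points", taking a rate of 50%. For subgroups: "Confidence interval widths for age, gender, and urban/rural subpopulations will range from ± 1.8 to ± 3.7". At alpha 0.05 it claims to detect an urban/rural difference "of 0.05 percentage points (i.e., 0.50 vs. 0.55) with a power of 0.83".
- **Medical Record Abstraction.** With 1,000 records the half-width is ±2.9 points, and the detectable urban/rural difference is "of 0.10 percentage points (i.e., 0.50 vs. 0.60) with a power of 0.89".

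Neither section states the test, its sidedness, the urban/rural split or an FPC, and no other section supplies them. The Aim 2 Analysis section stratifies indicator results and says the work will "determine whether that quality and completeness is consistent across selected subpopulations". It describes no variance adjustment for a finite population.

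Attachment B sets the scoring rules, including "All screener items must be nonmissing for a dependent item to be scored".

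**The concern.** Urban versus rural is the only contrast in the plan with a power figure, and Aim 2 sets out to judge consistency across subpopulations. If that comparison is run as an ordinary two-sided test and is not significant, a reader will weigh the result against the stated 0.83. If the real power is lower, the absence of a difference will look better supported than it is.

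Two features of the text raise the doubt. The power is higher than the usual formula gives at any split. The confidence intervals beside it are also narrower than 2,750 or 1,000 respondents ordinarily allow. In addition, the full-sample precision is promised for every survey indicator, while the scoring rules restrict most of them to subsets.

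**Working it through.** **Inputs** (Aim 2 sample-size sections): n = 2,750 of N = 8,080, rates 0.50 vs 0.55; n = 1,000, rates 0.50 vs 0.60; alpha 0.05. The split is not given, so it is varied.

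**1. Half-widths: where the plan's figures come from.** Half-width = 1.96 × 0.5 / √n, multiplied by √((N − n)/(N − 1)) if an FPC is used.

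- Survey: 0.98/√2,750 = 1.87 points. FPC = √(5,330/8,079) = 0.812, giving 1.52. Stated: 1.5.
- Record review: 0.98/√1,000 = 3.10 points. FPC = √(7,080/8,079) = 0.936, giving 2.90. Stated: 2.9.
- Subgroup ±1.8: without FPC this needs (0.98/0.018)² = 2,964 respondents. Even a value rounding down from 1.85 needs (0.98/0.0185)² = 2,806. Both exceed the 2,750 expected in total, so no subgroup can reach it. With FPC it needs 2,964 × (1 − 2,750/8,080) = 1,955, or 71% of the sample.
- Record-review subgroup ±3.6: with FPC this needs (0.98/0.036)² × (1 − 1,000/8,080) = 649, or 65% of the sample.

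The Handling Missing Data section puts the population at 8,000. That gives a survey FPC of √(5,250/7,999) = 0.810, a negligible change.

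**2. Power, ordinary two-sided test.** Power = Φ[(d − 1.96·SE0)/SE1], with SE0 pooled and SE1 unpooled. Survey at 50/50 (1,375 per group):

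- SE0 = √(2 × 0.525 × 0.475/1,375) = 0.01905
- SE1 = √((0.25 + 0.2475)/1,375) = 0.01902
- Φ[(0.05 − 0.03733)/0.01902] = Φ(0.666) = 0.747

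Unpooled, arcsine and continuity-corrected versions give 0.748, 0.747 and 0.735. With the FPC, both standard errors are multiplied by 0.812 (survey) or 0.936 (record review).

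| Split | Survey, no FPC | Survey, FPC | Records, no FPC | Records, FPC |
|---|---|---|---|---|
| 50/50 | 0.747 | 0.899 | 0.890 | 0.925 |
| 60/40 | 0.730 | 0.887 | 0.877 | 0.915 |
| 70/30 | 0.672 | 0.842 | 0.830 | 0.876 |
| 80/20 | 0.555 | 0.734 | 0.719 | 0.775 |

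Without FPC no split reaches 0.83. With FPC the survey gives 0.827 at 72/28 and record review gives 0.887 at 68/32, which round to 0.83 and 0.89. These shares lie close to the 71% and 65% implied by ±1.8 and ±3.6.

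**3. Size of the gap.** The chance of missing 0.50 vs 0.55 is 1 − 0.747 = 25% at best for the ordinary test, against 1 − 0.83 = 17%. Power 0.83 without FPC would need about 3,386 respondents at 50/50. With 2,750, the difference detectable at power 0.83 is 5.5 points at 50/50 and 6.0 at 70/30.

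**4. Indicators.** Counting sub-items within their parent and CC8c separately, Attachment B has 20 survey indicators. Only MH3a, SCP2 and SCP6 have no item screener. The other 17 are scored on subsets.

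**The case against.** The best defence is that nothing was miscalculated. A two-sided test with an FPC for 8,080 reproduces both powers and the half-widths at plausible splits. Aim 2 concerns a fixed cohort in which every caregiver is invited, and for describing that cohort an FPC is arguable. Self-selected response does not by itself favour ordinary standard errors, since they too assume that response is uninformative. The intention "The results of this research have real potential to be implemented in other settings, namely in other ACOs" sits in the Dissemination Plan and covers the whole project, so it does not define Aim 2's inferential target. The Analysis section speaks of stratifying and does not say that a non-significant result will be read as consistency.

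Most of this stands, and it rules out stronger readings:

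- *That 0.83 is an error.* The documents do not show this; an undeclared FPC explains it.
- *That a one-sided test was used.* Nothing in the text suggests it, and without an FPC it could not explain the half-widths.
- *That 0.83 and 0.89 contradict each other because no single split yields both.* The plan does not say that the survey and record-review samples share a split, and the 1,000 are consenters. Even at a common 70/30 the FPC gives 0.842 and 0.876, so the mismatch is of rounding size.

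What the defence does not settle is the test. An FPC shrinks the error of a description of these 8,080 children, and would take it to zero at full response. An ordinary significance test for an urban/rural difference does not use it, and the plan does not say that its test will.

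**Conclusion.** The concern holds as an undeclared assumption. As written, an ordinary two-sided urban/rural comparison would have power of at most 0.75 for 0.50 vs 0.55, and about 0.67 at an illustrative 70/30, against the stated 0.83. The 25% miss rate is conditional on a test without FPC; with the FPC and about 72% in the larger group, the stated 17% is right.

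The shortfall applies near a 50% rate, close to the least favourable case. At equal groups the ordinary test has power 0.88 for 0.20 vs 0.25 and 0.93 for 0.80 vs 0.85. The record-review 0.89 is met without FPC only near 50/50.

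The full-sample half-width and power do not apply to the 17 screened indicators. How far they fall short cannot be computed, because the documents give no screened numbers. Writing 0.05 and 0.10 percentage points is a unit slip that the rates in brackets resolve.

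Aim 3 is not affected. Non-response bias is a separate matter, left to the analyses under Handling Missing Data. The point should be fixed because the figure bears on a stated purpose of Aim 2 and correcting it is cheap.

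**What to change.** In the two Aim 2 Participants & Sample Size sections:

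1. State the sidedness, the assumed urban/rural split and whether an FPC was used.
2. Give the ordinary two-sided power as the figure for the significance test. For the survey this is at most 0.75, or about 5.5 points detectable at power 0.83 with equal groups. For record review it is 0.89 near 50/50 and about 0.83 at 70/30. Any FPC-based power for the fixed cohort can stand beside it, labelled as such.
3. Either give half-widths of ±1.9 and ±3.1 and recompute the subgroup ranges, or declare the FPC and limit those widths to describing the 8,080-child cohort under random non-response.
4. Replace 'each' indicator with 'each indicator scored on all respondents'.
5. Write 5 and 10 percentage points.

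The cost is wording only. Enrolment does not change, because all 8,080 are already invited. The downside is that the stated precision and power become less favourable.

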The underlying population for this study is all children up to age 18 enrolled in the Partners for Kids (PFK) on May 30th 2015 who had been previously enrolled in fee-for-service (FFS) Medicaid and transitioned into PFK as a result of the ABD policy change. The primary analytic data comes from Ohio Medicaid administrative claims. Claims data have different missing data issues than do other primary or even secondary data sets on several dimensions. First, many of the fields are mandatory, which means fields such as procedure code and Medicaid eligibility status will

be 100% complete. Second, although claims data have the traditional limitations of any administrative data, including the lack of information of services paid fully out-of-pocket or financed through Medicare, only services provided through Medicaid will be used in the analysis, which will take a Medicaid/agency perspective. This means that services and expenditures will not aim to be a complete record, but those covered through the Medicaid program. We will clearly indicate the scope of analysis in publications. For the subsets of claims data merged with survey and medical records, we do not anticipate missing data problems for the same reasons above.

The estimated size of this population is 8,000. Because of the qualitative nature of Aim 1 we do not propose a missing data plan. The following assumptions have been made regarding rates of participation from this population for Aims 2 and 3:

Aim 2 – Caregiver Survey

We expect 34% percent of the eligible caregivers to complete the caregiver survey. This is based on assumptions from previous studies with this population regarding degree of incorrect addresses for the opt-out mailing, opt outs, missing/non-functional telephone numbers, and refusal when contacted.

- *Prevention of missingness*– We will use alternative sources of contact information (e.g. EHR records, internet look-up sites) for those families with missing telephone numbers.
- *Monitoring of missingness* – we will record and report the following statistics: % of invitation letters returned by the post office, % opting out, % bad telephone numbers that cannot be found after research, and % refusal by reached families. For each of these percentages, we will describe the lost respondents by gender, age, urban/rural residence, and diagnosis category using PFK data (note: race is not reliably available on the PFK data).

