We expect 35% percent of those completing the telephone survey to consent to medical record abstraction.

- *Prevention of missingness* – The script requesting medical record access will clearly explain the reason for access and the processes for maintaining confidentiality.
- *Monitoring of missingness*– We will describe the lost respondents by gender, age, urban/rural residence, and diagnosis category using claims data. We will also test the relationship between perceptions of care coordination and consent to medical record abstraction using data from the telephone survey.

A consort-style diagram will be used to illustrate potential participant loss or refusal at each stage of the study **(MD-4)**.

Aim 3 – Utilization Analysis

Over 95% of the population will be included in claims data analysis looking at overall pre-/post-policy change utilization analysis. The primary risk of missingness for this analysis is failure of successful linking between the FFS (pre) and PFK (post) data. After acquisition of the data, we will first assess the data quality. Like the traditional Medicaid plan, PFK reimburses physicians

on the basis of services provided (fee-for-service), therefore we expect that the payment data and other fields such as patient id, date of service, and procedure codes required for reimbursement will be populated for each claim billed to Medicaid/PFK. The demographic files (e.g. gender, race) may also have missing data, which is anticipated to be proportionally small, based on the team's prior experience with claims.

- Prevention of missingness – We will investigate each non-match. When there is no matching Medicaid ID across the two databases, we will directly check the record to identify potential transposition or typographical errors. If no such error can be found, we will attempt to use probability matching using date of birth, zip code of residence, gender, and soundex last name to link records.
- Monitoring of missingness– We will calculate and report the final “no-match” rate between PFK and state FFS data.

Statistical methods and sensitivity analysis to handle missing data (MD2, MD3, MD5)

Aim 2 – Caregiver Survey

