Based on our pilot work, we expect that 1,000 caregivers who complete the phone survey will also provide consent for abstraction of their medical records for MR based care coordination measures. Data for Medical record-based care coordination measures will be collected primarily through review of the Epic EMR at Nationwide Children’s Hospital (NCH) conducted by an experienced, trained NCH abstractor using a field-tested data abstraction tool. The integrated EMR at NCH allows review of NCH inpatient visits and primary and specialty care services provided by physicians in the NCH system. We estimate 50% of ABD children enrolled in PFK were seen in the NCH system in the past year. If a participant lists a main provider outside of the NCH system, a copy of the relevant medical records will be requested from that provider for review. The first 20 records will be re-reviewed by a second abstractor for quality control and training.

Aim 3

Assumptions

- PFK data and claims data are housed on servers at NCH.

- NCH has permission from PFK to use data.
- NCH has permission from the state to use data.
- NCH will provide a limited de-identified dataset at the person-month level.
- Data will be provided in SAS and STATA format.
- Data will be available for download from a secure server using a double-password system.
- [name], [name], [name], [name], and the NCH programmer will have access to the data.

Steps for Data Preparation and Access

1. [name] and [name] will develop a programming guide for the programmer.
2. NCH Programmer links PFK and state data (EHR data, claims data) to study data (caregiver data) and strips identifiers.
3. NCH Programmer creates an analytic file.
4. NCH Programmer runs frequencies.
5. NCH Programmer makes de-identified dataset available in both SAS and Stata formats.
6. NCH will notify team that data are available for download.
7. [name] will log on to server using double-password system (VPN-like system).
8. [name] will download and house data on secure site at UNC & OSU.

Dissemination Plan

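### The record-review sample of 1,000 conflicts with the plan's own 35% consent rate (about 962), and the precision and power figures count consents as abstracted charts

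*Combined protocol and SAP*

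**What the plan says.** Four parts of the combined protocol and SAP bear on this.

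- **Aim 2, Caregiver Survey, Participants & Sample Size.** The survey is offered to the caregivers of the full group of 8,080 children. The expected return is given as: "We estimate that our methods will yield 2,750 caregiver survey respondents".
- **Aim 2, Medical Record Abstraction, Participants & Sample Size.** The number expected for this step is put as follows: "We further estimate that 1,000 of those who complete the survey will consent to a review of their medical records". With that number as the sample size, the section gives a 95% half-width of ±2.9 points at 50% performance, subgroup half-widths of ±3.6 to 7.0, and power of 0.89 to detect 0.50 versus 0.60 between urban and rural children. It does not state the urban/rural split or whether a finite-population correction (FPC) was used.
- **Handling Missing Data.** "The estimated size of this population is 8,000", and for the record review, "We expect 35% percent of those completing the telephone survey to consent to medical record abstraction".
- **Procedures, Aim 2, Medical Record Review.** The 1,000 returns: "we expect that 1,000 caregivers who complete the phone survey will also provide consent for abstraction of their medical records". Abstraction is mainly from the NCH electronic record. The section adds: "We estimate 50% of ABD children enrolled in PFK were seen in the NCH system in the past year". Where the participant names a main provider outside that system, "a copy of the relevant medical records will be requested from that provider for review". No retrieval rate is given.

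The Aim 2 Analysis section expects little missing data in the record review and uses available-case analysis, so a chart that is not obtained drops out.

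**The concern.** There are two separate issues. First, the plan gives two consent figures that do not agree, and the precision and power use the larger one. Second, precision depends on the number of charts abstracted, whereas the number entered is the number of caregivers who consent. The two are equal only if every outside provider supplies the chart, and the plan neither says this is expected nor allows for a shortfall.

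At stake are the stated precision of every record-based indicator and the power of the one subgroup comparison that the section sizes. Chart source also affects interpretation. The NCH record is integrated across inpatient, primary and specialty care, while an outside chart is a copy from one provider. If the two differ in completeness, a reader would want indicators shown by source, and the plan does not say that source will be recorded.

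**Working it through.** **Inputs from the plan.** Population N = 8,080 (8,000 in the missing-data section); survey respondents 2,750, at a 34% response rate; record-review sample 1,000; consent rate 35%; performance 0.50; contrast 0.50 versus 0.60; alpha 0.05, taken as two-sided. I apply the 35% to all 2,750 respondents, although the text ties it to telephone completers. That reading favours the plan.

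**Step 1: reproduce the plan's figures at n = 1,000.**

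Half-width = 1.96 × √(0.25/n) × √((N − n)/(N − 1))

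- With the FPC: 1.96 × √(0.25/1,000) × √(7,080/8,079) = 3.10 × 0.936 = 2.90 points. This matches ±2.9.
- Without the FPC: 3.10. The plan therefore appears to use the correction.

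Power, for m children per group, is Φ[(0.10 − 1.96 × √(2 × 0.55 × 0.45/m)) / √((0.25 + 0.24)/m)].

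- With m = 500 (equal split, no FPC): 0.890. This matches 0.89.
- With the FPC and a split of about 67/33, the result is also 0.89, so the basis cannot be identified from the text.

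**Step 2: the consent rate.**

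- 1,000/2,750 = 36.4%.
- 0.35 × 2,750 = 962.
- 0.34 × 0.35 × 8,000 = 952.

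**Step 3: the same formulas at the 35% rate.**

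| n | Half-width, FPC | Half-width, no FPC | Power, equal split, no FPC |
|---|---|---|---|
| 1,000 | 2.90 | 3.10 | 0.890 |
| 962 | 2.97 | 3.16 | 0.878 |
| 952 | 2.98 | – | 0.874 |

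On the alternative basis (67/33 with the FPC), 962 gives 0.879. At least 972 records are needed for the half-width to round to 2.9. The subgroup half-widths scale by 2.97/2.90 = 1.024, so 3.6 to 7.0 becomes about 3.7 to 7.2.

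**Step 4: chart yield (illustration, not derived from the plan).** Assume that half of the 962 consenters need an outside chart and that a fraction r is obtained. Then n = 962 × (0.5 + 0.5r).

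| r (assumed) | Charts | Half-width, FPC | Power, equal split, no FPC |
|---|---|---|---|
| 100% | 962 | 2.97 | 0.88 |
| 80% | 866 | 3.15 | 0.84 |
| 60% | 770 | 3.36 | 0.80 |
| 50% | 722 | 3.48 | 0.77 |
| 0% | 481 | 4.33 | 0.60 |

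Power at an equal split falls below 0.80 under about 776 charts. In this illustration that is r below about 61%: 776/962 = 0.807, and (0.807 − 0.5)/0.5 = 0.61.

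**The case against.** The strongest reply is that nothing of substance is wrong. Both stated figures reproduce at 1,000. The only change the documents themselves support, from 1,000 to 962, costs 0.07 points of half-width and 0.01 of power. Both 1,000 and 35% are offered as expectations, and 35% may be a rounded figure. The plan also promises a participant-flow diagram of loss at each stage, a description of lost respondents by urban/rural residence, a field-tested abstraction tool and a trained abstractor. Most of this stands, and the consent discrepancy alone does not threaten the design. However, the diagram would show chart loss only afterwards, and the monitoring described for this step concerns refusal of consent rather than charts that never arrive.

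Three stronger readings are tempting, and the documents do not support them.

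- **That half the consenters need outside charts.** The 50% describes children in the Partners for Kids (PFK) plan seen at NCH in the past year. The trigger for a request is a main provider outside NCH. A child seen at NCH may have an outside main provider, and a child not seen there recently may name an NCH one. Nor is 50% a rate among consenters.
- **That the consent rate brings power down to about 0.82.** That value needs an assumed 70/30 split without the FPC, under which 1,000 charts already give 0.83.
- **That chart source creates a false urban/rural gap.** No passage says that outside charts score lower or that rural children use NCH less. Any figure for such a gap rests wholly on assumed inputs.

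**Conclusion.** The inconsistency is real and its direct effect is small: 962 rather than 1,000 consents, about ±3.0 rather than ±2.9, and 0.88 rather than 0.89. This holds on either basis that reproduces the plan's power. A reader might infer that the design falls materially short of its stated precision and power. The documents do not show that, because any material loss would have to come from chart retrieval, for which they give no figure.

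What the documents do show is that consents stand in for charts with no allowance for yield. The resulting loss can be ranged but not derived, and the table of assumed retrieval rates is an illustration resting on an assumed half needing outside charts. The possibility that chart source affects the urban/rural comparison is a reason to record source. It is not evidence of bias.

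**What to change.** 1. Use one consent rate in the Medical Record Abstraction sample-size section, the missing-data section and the Medical Record Review procedures.
2. Restate the half-width, subgroup ranges and power for the expected number of abstracted charts. State the assumed share of consenters needing outside charts, the assumed retrieval yield, whether the FPC is applied, and the urban/rural split.
3. Record chart source (NCH electronic record or outside copy) at abstraction, and report the record-based indicators, including the urban/rural comparison, by source as a sensitivity analysis. I would not adjust the main urban/rural contrast for source: the aim is descriptive, and where a child receives care may be part of why the groups differ.

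The cost is slightly less favourable stated figures, one field recorded at abstraction and one extra tabulation. No additional charts or staff are needed.
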